### **11.5.3 ACTH Stimulation Test**

The proportion of subjects with abnormal serum cortisol response for ACTH stimulation test at the end of treatment (cortisol level  $\leq 18$  ug/dL at 30 minutes post stimulation) will be summarized by treatment group. Additionally, the serum and saliva cortisol levels found pre-stimulation and post-stimulation will be summarized for the screening ACTH test and the end of treatment ACTH test. The sample size N, mean, median, standard deviation, minimum, and maximum saliva cortisol levels will be provided for the subsets of subjects with abnormal and normal serum cortisol response.

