**Safety criteria:**

The proportion of subjects with abnormal serum cortisol response for ACTH stimulation test at the end of treatment (cortisol serum level  $\leq 18$  ug/dL at 30 minutes post stimulation) is the primary safety variable.

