The potential for HPA axis suppression of DFD-01 has been studied in adults with moderate to severe psoriasis ([Study BDS1307](#)). After 15 and 29 days of treatment, 20.8% (5 out of 24) and 0% (0 out of 24) of subjects had abnormal cortisol levels in the ACTH stimulation test, respectively. This study is to determine the potential for HPA axis suppression and extent of systemic drug exposure in the adolescent population with moderate to severe psoriasis.

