### **7.6 Early Withdrawal of Subjects**

1. Subjects should be withdrawn from the study if they or their legal guardian no longer wish to participate, are being uncooperative, or if the investigator feels that it is in the best interest of the subject to withdraw.
2. Subjects with protocol deviations or for whom it is discovered should have been excluded should not be withdrawn unless there is a safety concern. The protocol deviation should be recorded in the subject's chart and Sponsor Consultation form.

3. Subjects who experience an AE resulting in or requiring discontinuation of study product use should be encouraged, in conjunction with their legal guardian, to be followed until the AE is resolved or stabilized.
4. If a female subject becomes pregnant during the study, study product will be discontinued immediately and she will be followed through the pregnancy and delivery. Details of the pregnancy, delivery and health of the infant should be recorded on the Pregnancy Surveillance Form and the sponsor notified immediately.
5. At the time of study discontinuation, the investigator will record the reason for early withdrawal, date of last study product application, date of last visit or contact, collect adverse event data, and, if possible, perform all End of Treatment Visit specific evaluations. Every attempt should be made to contact subjects who are lost-to-follow-up via their legal guardian for a final safety assessment. At least three attempts must be documented in the subject's chart including the use of at least 1 certified letter. Any contact, either direct or indirect, should be made with the purpose to document the final status of the subject with regard to safety.
6. Subjects who withdraw early will not be replaced.

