### **7.9 Study Schedule**

Study Schedule charts can be found on pages [7](#) and [8](#). There are at least 4 or 5 study visits; Screening (Visit 1), Baseline (Visit 2, Day 1), Day 8 (Visit 3), Day 15 (Visit 4 – End of Treatment Visit for the 15-day treatment group), and Day 29 (Visit 5 – End of Treatment Visit for the 29-day treatment group). A supplemental Visit 5 or 6 (Day 43 or 57) may be required to repeat the ACTH stimulation test if it was abnormal at the End of Treatment Visit.

This is a short trial and it is imperative that subjects and their legal guardians understand the importance of attending each visit as scheduled. This should be discussed with the subject and legal guardian before randomization at Visit 2. Randomized subjects and legal guardians must be counseled to keep all scheduled appointments and to return to the site within the permitted visit windows for each treatment visit ( $\pm$  3 days for Visits). If a subject misses a visit, they and their legal guardians, should be encouraged to attend the next visit scheduled from the Baseline

---

Visit (Visit 2) date. It is especially important for the subject to complete the End of Treatment evaluation.

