## **11 STATISTICAL CONSIDERATIONS**

All statistical processing will be performed using SAS® unless otherwise stated. Descriptive statistics will be used to summarize the data. No inferential testing will be performed. All summaries will be performed on the safety population.

No interim analyses are planned.

No imputations will be made for missing data.

A Statistical Analysis Plan, describing all statistical analyses, will be provided as a separate document prior to database lock.

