### **11.5 Safety Summaries**

Descriptive statistics will be presented to summarize the safety data. Continuous variables will be summarized with sample size N, mean, median, standard deviation, minimum, and maximum. Categorical variables will be summarized with sample size N, frequency counts and percentages.

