### **11.5.4 Pharmacokinetics**

The plasma concentrations of betamethasone, betamethasone-17-propionate, and betamethasone-17,21-dipropionate will be summarized (and will include 95% confidence intervals for the mean) for the PK Screening sample and for 0 (pre-treatment), 1, 3, and 6 hours ( $\pm 5$  minutes) after the last application of study product at the end of treatment. The average of the post-treatment concentrations will also be summarized. Plasma concentrations that are taken more than 1 hour off-schedule will be included in data listings only and will not be included in the summarization of the concentration data.

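### The primary safety proportion is planned as N, count and percentage with no confidence interval, so an arm with 0 of 25 abnormal tests would be reported as 0% without its exact 95% upper limit of 13.7%

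*Combined protocol and SAP*

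**What the plan says.** The Synopsis (Safety criteria) says of the proportion with serum cortisol at or below 18 ug/dL 30 minutes after stimulation, at the end of treatment, that it "is the primary safety variable". Section 11.5.3 returns to "The proportion of subjects with abnormal serum cortisol response for ACTH stimulation test at the end of treatment" and says only that it is summarised by treatment group. The statistics to be shown come from Section 11.5: "Categorical variables will be summarized with sample size N, frequency counts and percentages".

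Section 11 describes the analysis as descriptive, rules out inferential testing, and leaves the full analyses to a separate Statistical Analysis Plan due before database lock. On missing data it states: "No imputations will be made for missing data". Section 11.1 sets 25 subjects per group and says that this number has no statistical justification.

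The statistical section plans one kind of interval. In Section 11.5.4 the plasma concentrations will be summarised "and will include 95% confidence intervals for the mean".

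The Introduction gives the adult experience after 15 and 29 days, in that order: "20.8% (5 out of 24) and 0% (0 out of 24) of subjects had abnormal cortisol levels in the ACTH stimulation test".

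**The concern.** The first objective is to evaluate how far the product can suppress the HPA axis in adolescents under maximal use. The primary safety variable answers that question through one proportion per arm, from about 25 subjects. At that size the percentage alone says little about which suppression rates remain plausible. This matters most when the count is zero, because 0% reads as reassurance when it is only the point estimate.

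The descriptive framework does not explain the omission. An interval is estimation, not a test, and the plan already uses intervals for mean drug concentrations. The supporting PK measure therefore gets a stated precision and the primary safety variable does not. Section 11.1 offers no precision statement at the design stage either.

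**Working it through.** **Inputs.** 25 per arm (Section 11.1); at most 65 randomised (Section 5.1); adult counts 5/24 and 0/24 (Introduction). The 95% level matches the one in Section 11.5.4.

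**The protocol's own figures.** 50 / 2 = 25 per arm. 5/24 = 20.8% and 0/24 = 0%. All reproduce. The 25 rests on no alpha, power or precision target, so it cannot be re-derived further.

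**Zero events.** The two-sided exact (Clopper-Pearson) 95% upper limit solves (1 - p)^n = 0.025, so p = 1 - 0.025^(1/n). For n = 25: 1 - 0.025^(1/25) = 0.1372, or 13.7%.

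**Non-zero counts.** With x events in n, the lower limit is the 0.025 quantile of Beta(x, n - x + 1) and the upper limit is the 0.975 quantile of Beta(x + 1, n - x).

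| Result | Percentage | Exact 95% limits |
|---|---|---|
| 0/25 | 0% | 0% to 13.7% |
| 1/25 | 4% | 0.1% to 20.4% |
| 5/25 | 20% | 6.8% to 40.7% |
| 0/24 (adult, 29 days) | 0% | 0% to 14.2% |
| 5/24 (adult, 15 days) | 20.8% | 7.1% to 42.2% |

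**How often zero would occur.** If the true rate were 10%, the chance of 0/25 is 0.90^25 = 0.072. If it were 5%, the chance is 0.95^25 = 0.277.

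**Sensitivity to n.** With zero events the upper limit is 16.8% if only 20 in an arm are tested (an assumed figure). It is 10.9% or 10.6% at 32 or 33 per arm, which is the 65-subject cap divided by two.

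**Sensitivity to method.** For 0/25 the upper limit is 13.3% by Wilson, 12.0% by the rule of three, and 11.3% by the one-sided exact 95% method. All lie well above zero.

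**Denominator.** Assume 4 abnormal results and a safety population of 25, of whom 1, 3 or 5 were not tested. Then 4/25 = 16.0% becomes 4/24 = 16.7%, 4/22 = 18.2% or 4/20 = 20.0%. The largest shift is 4 points. The exact interval for 4/25 runs from 4.5% to 36.1%, about 32 points wide, so the denominator matters much less than the missing interval.

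**The case against.** Four points can be made for the plan.

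- **The SAP may already contain the interval.** The protocol defers its analyses to a separate document that was not available. A reader might infer that the trial will report no interval at all, but the documents do not support that. They show only that the protocol's stated summary has none.
- **The information is not lost.** Section 11.5 requires N and the count, so the table would read 0 of 25 (0%), not a bare 0%. Anyone can compute the limit from those two numbers. This stands, and it limits the harm to what the printed table conveys.
- **The study is openly descriptive.** It has no threshold, comparison or decision rule for an upper limit to feed. That is true, but the intervals in Section 11.5.4 show that ruling out testing does not rule out intervals.
- **The denominator is largely settled.** Section 11.2 admits subjects to the safety population without an end-of-treatment ACTH result, and Section 7.6 asks staff at early withdrawal to "if possible, perform all End of Treatment Visit specific evaluations". A reader might infer that untested subjects will be counted as not suppressed and the rate understated. The documents do not support that. Section 11.5.3 defines abnormal by a measured 30-minute value, and the no-imputation rule argues against assigning an outcome to an untested subject. Section 7.9 also presses for complete testing: "It is especially important for the subject to complete the End of Treatment evaluation". What remains is a small gap in wording: the denominator is not stated, nor is whether a test done at early withdrawal counts as an end-of-treatment test.

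**Conclusion.** The concern holds as a gap in the protocol's reporting of its primary safety variable. The stated summary is N, count and percentage by arm, with no interval and no precision basis for 25 per arm. A zero result would be printed as 0 of 25 (0%) without showing that rates up to 13.7% remain compatible with it. A 20% result would be printed without its limits of 6.8% and 40.7%.

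These figures assume that all 25 subjects in an arm are tested and that two-sided exact 95% limits are used. Fewer tested subjects would raise the upper limit for a zero count. The 0/25 result is illustrative, though 0/24 in one adult arm makes it plausible.

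The finding is limited to the protocol and does not show a biased estimate. The denominator and early-withdrawal wording is a minor clarification.

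**What to change.** In Section 11.5.3, and in the separate SAP if it is not already there, state that each arm's abnormal proportion will be reported with a two-sided exact (Clopper-Pearson) 95% confidence interval. Base it on safety-population subjects with an end-of-treatment 30-minute serum cortisol result, and show the number untested in each arm.

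As a clarification, add one sentence saying whether tests done at early withdrawal are included. A sentence in Section 11.1 giving the precision of 25 per arm, for example the 13.7% upper limit for 0/25, would be useful but is optional.

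The cost is a few lines of text and code on data already collected. The downside for the sponsor is a less favourable displayed upper limit. No hypothesis test or design change is needed.

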There are many approved topical products containing betamethasone dipropionate on the market in the USA indicated for the treatment of corticosteroid responsive dermatoses such as psoriasis and atopic dermatitis. The first product was approved in 1975. Adverse events associated with the use of topical betamethasone dipropionate include erythema, folliculitis, pruritus, and vesiculation each occurring in less than 1% of patients.

In addition, the following additional local adverse reactions have been reported with topical corticosteroids, and they may occur more frequently with the use of occlusive dressings and higher potency corticosteroids. These reactions are listed in an approximately decreasing order of occurrence: burning, itching, irritation, dryness, folliculitis, hypertrichosis, acneiform eruptions, hypopigmentation, perioral dermatitis, allergic contact dermatitis, secondary infection, skin atrophy, striae, and miliaria.

DFD-01 contains 0.05% betamethasone dipropionate (potency expressed as betamethasone) in a convenient, cosmetically elegant spray formulation. The inactive ingredients are commonly

---

used excipients for topical products. More information about DFD-01 can be found in the Investigator's Brochure.

The current clinical study is intended to evaluate the potential for HPA axis suppression of this new formulation of betamethasone dipropionate in adolescent subjects with moderate to severe psoriasis. Exogenous corticosteroids can suppress the HPA axis, resulting in decreased circulating adrenocorticotropic hormone (ACTH) levels, atrophy of glucocorticoid-secreting cells in the adrenal cortex, and secondary adrenal insufficiency. HPA axis suppression will be determined from the results of an ACTH stimulation test.

The ACTH stimulation test measures how well the adrenal glands respond to the hormone ACTH. ACTH is a hormone produced in the pituitary gland that stimulates the adrenal glands to release cortisol. A normal response is a serum cortisol level of more than 18 ug/dL 30 minutes after the ACTH is injected. Cortisol can also be reliably measured in saliva ([Gallagher, 2006](#)) but the criteria for a normal response to ACTH has not been established. Both serum and saliva cortisol will be measured in this study to provide data about the saliva level criterion for a normal response.

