### **11.1 Sample Size**

Approximately 50 subjects will be randomized to the two treatment groups in a 1:1 ratio for 25 subjects per group. No statistical justification has been made for the sample size.

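### Saliva cortisol is sampled to inform a criterion for a normal ACTH response, but Section 11.5.3 plans only descriptive summaries and no serum-saliva association

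*Combined protocol and SAP*

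**What the plan says.** The Introduction states that for saliva "the criteria for a normal response to ACTH has not been established", and continues: "Both serum and saliva cortisol will be measured in this study to provide data about the saliva level criterion for a normal response". No other reason for saliva sampling is given. Saliva appears in neither statement of objectives (Synopsis; Section 3), and the primary safety variable is serum cortisol alone.

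Section 11.5.3 plans two saliva summaries. The first is overall: "the serum and saliva cortisol levels found pre-stimulation and post-stimulation will be summarized for the screening ACTH test and the end of treatment ACTH test". A second summary is by serum response. Its six statistics run from the number of subjects to "maximum saliva cortisol levels will be provided for the subsets of subjects with abnormal and normal serum cortisol response". Nothing there says which visit, or which of the two saliva samples, this second summary uses. Section 11.5.8 says that there are no subset analyses, which sits awkwardly beside it.

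Section 11 makes the study descriptive, rules out inferential tests, and defers full detail to a separate SAP due before database lock. No text of that SAP is among the documents reviewed. On size, Section 11.1 says "Approximately 50 subjects will be randomized to the two treatment groups in a 1:1 ratio for 25 subjects per group" and "No statistical justification has been made for the sample size".

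**The concern.** A saliva criterion has to be tied to the serum threshold of 18 ug/dL at 30 minutes. The information for that lies in how saliva moves with serum, above all near 18. The planned table reduces serum to two classes, so a subject at 18.5 counts the same as one far above the threshold. What the table says about a criterion then rests mainly on the abnormal class.

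That class will be small. Section 5.2 requires a normal screening test, so abnormal responses in randomized subjects can arise only after treatment starts. At stake is how much the saliva samples taken from every subject can tell about a criterion. No primary result and no subject's safety is affected.

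**Working it through.** **Inputs.** The Introduction gives the adult study's result: "20.8% (5 out of 24) and 0% (0 out of 24) of subjects had abnormal cortisol levels in the ACTH stimulation test", after 15 and 29 days respectively. Section 11.1 gives 25 subjects per group. Sections 5.2 and 7.5.1 set normal as serum above 18 ug/dL at 30 minutes. The documents give no saliva means, SDs or serum-saliva correlation.

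**The plan's own figures.** 5/24 = 20.8% and 0/24 = 0%, as stated. The sample size has no calculation behind it to reproduce.

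**Expected abnormal subjects at end of treatment**, assuming adult rates hold in adolescents:
- 25 × 5/24 + 25 × 0/24 = 5.2 of 50. At the cap of 65 subjects: 32.5 × 5/24 = 6.8.
- Binomial(25, 5/24): 95% range 2 to 9.
- The adult rates are themselves uncertain. Exact 95% intervals are 7.1% to 42.1% for 5/24 and 0% to 14.2% for 0/24. A beta-binomial prediction with Jeffreys priors gives a median of 6 and a 95% range of 1 to 13.

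**What the abnormal subset can show.**
- Mean of 5 values: the 95% CI half-width is t(0.975; 4)/√5 = 2.776/2.236 = 1.24 SD.
- Sensitivity when all k abnormal subjects are caught: the exact lower limit is 0.025^(1/k). For k = 5 it is 0.478; for k = 13 it is 0.753. It first reaches 0.80 at k = 17.
- With k = 1 the planned SD is undefined.
- Specificity is less of a problem: 45/45 gives a lower limit of 92.1%.

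**Would a ROC cut-off do better in the same subjects?** No. Simulation of the Youden cut-off with 5 abnormal and 45 normal subjects (equal-variance normal, 3,000 runs), with assumed separations:

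| Assumed separation | True best cut-off | 95% range of chosen cut-off | Sensitivity at true best cut-off | 95% range of true sensitivity at chosen cut-off |
|---|---|---|---|---|
| 2 SD | 1.0 SD | −0.12 to 1.69 SD | 84% | 45% to 95% |
| 3 SD | 1.5 SD | 0.30 to 2.13 SD | 93% | 62% to 98% |

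**What the paired data hold.** With complete data there are 50 × 2 = 100 post-stimulation pairs (screening and end of treatment), plus any recovery tests. Counting pre-stimulation pairs gives 50 × 2 × 2 = 200, but the criterion concerns the 30-minute value, so the 100 are the relevant ones. Withdrawn subjects are not replaced (Section 7.6), so both are upper figures apart from recovery tests.

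**Direction of the regression.** The 50 screening post-stimulation values are selected on serum above 18. If serum is the outcome, that selection can bias the line near 18, and reading off the saliva value at serum 18 is inverse prediction. If saliva is the outcome and serum the covariate, selection is on the covariate, which does not bias a correctly specified line, and the saliva level at serum 18 is a direct estimate.

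**The case against.** The strongest reply is that the plan does what it says. The Introduction speaks of providing data about a criterion, not of establishing one, and descriptive saliva values by serum response are such data. This stands, and it keeps the severity low.

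Four stronger readings are tempting, and the documents do not support them.
- A reader might infer that only subset means are planned. The table also gives the median, SD, minimum and maximum. The extremes show whether the two classes overlap and, if they do not, crudely bracket a cut-off.
- A reader might infer that the pairing is thrown away. Sorting each saliva value by the same subject's serum response uses the pairing, but in dichotomised form.
- A reader might infer that no other analysis will be done. That can be said of the protocol text only, since Section 11 leaves detail to the SAP.
- A reader might infer that 200 pairs settle the matter. Half are pre-stimulation, and nothing in the documents supports one common serum-saliva relation before and after stimulation.

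It may also be said that a model does not belong in a descriptive study. Estimation with an interval is not a test, and Section 11.5.4 already plans 95% confidence intervals for mean plasma concentrations.

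**Conclusion.** The point holds as a mismatch between a stated purpose and a thin analysis. The protocol text plans only descriptive saliva summaries, and with about 5 abnormal subjects (roughly 1 to 13) the subset table can bracket a criterion only crudely. The conclusion does not hang on the figure of 5: even 13 of 13 caught leaves a lower limit for sensitivity of 75%. It does assume that adult rates are a fair guide to adolescents.

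A paired, continuous analysis is better because every post-stimulation pair contributes, not only the abnormal ones. How precise it would be cannot be computed from the documents; that depends on the saliva scatter and on how many serum values fall near 18. It would estimate the average saliva level at serum 18, not a cut-off with proven sensitivity.

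The documents do not support saying that the trial fails an objective. Severity is low: an improvement worth making, not a defect in the primary analysis.

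**What to change.** In Section 11.5.3, or in the SAP before database lock, add for randomized subjects:

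1. A scatterplot of paired 30-minute post-stimulation serum and saliva cortisol from screening, end of treatment and any recovery tests, with the serum threshold marked.
2. A regression of saliva on serum with a subject random effect, reporting the estimated saliva level at serum 18 ug/dL with a 95% CI. Check the form of the relation on the plot.
3. Pre-stimulation pairs shown separately or as a sensitivity analysis, not pooled by default.
4. Any sensitivity, specificity or ROC summary labelled exploratory, with exact intervals.
5. A statement of which visit and which saliva sample the existing subset table uses, and wording in Section 11.5.8 that allows for that table.

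For randomized subjects this is free: the samples are already planned and only a small analysis is added. Including screen failures is optional and is not free. Section 7.2 captures only limited fields for them, and Section 11.2 confines summaries to dosed subjects with post-baseline safety data, so extra CRF fields and a separate analysis set would be needed. The documents do not say how many there would be.
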